9.1.3.2 Gene Expression Profiling

Additional biopsy for fresh tissue sample is not required in this study. We will use the cDNA-mediated Annealing, Selection, Extension, and Ligation (DASL) assay from Illumina which has been developed to allow more comprehensive gene expression profiling of degraded RNA extracted from paraffin blocks using bead array format as previously described³⁷. Illumina's Bead Array Technology is based on 3-micron silica beads that self assemble in microwells on either of two substrates: fiber optic bundles or planar silica slides. When randomly assembled on one of these two substrates, the beads have a uniform spacing of ~5.7 microns. Each bead is covered with hundreds of thousands of copies of a specific oligonucleotide that act as the capture sequences in one of Illumina's assays. BeadArray technology is utilized in Illumina's iScan System for a broad range of DNA and RNA analysis applications.

All promising findings of gene expression changes will also be validated by the quantitative RT-PCR methods. Change in expression of genes as a result of treatment will be determined by IHC or quantitative RT-PCR. Although IHC can be easily accomplished on a single slide, it may not be sensitive to small changes in expression and expression measurements are semi-quantitative. Quantitative (real-time) RT-PCR can provide better quantification of expression of gene product, and recent studies have shown that this approach can be applied to RNA isolated from paraffin-embedded tissues, when small sequences are amplified. The overall goal of these studies is to identify candidate markers for response and molecular profiles that might be relevant to an understanding of drug mechanisms. Although statistical methods will provide some indication of significance of particular molecular changes, validation will ultimately require additional testing in independent samples.

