- 12.5.4 For the global gene expression analysis, we will have tissue samples from between 12-41 women enrolled in this study. Each of the tissue samples will be preprocessed using DASL assay from Illumina as described above. The resulting CEL files will be imported and stored on the Gene Traffic database in the Biostatistics Core (Core 4). Gene Traffic software will be used for quality control and identification of any experimental artifacts, including spatial patterns on chips. GCRMA will be applied to the CEL file results using the "Affy" library within the Bioconductor suite using R statistical software.⁴⁸ The GCRMA method summarizes probe set information to obtain one gene expression measurement per probe set on the array. Significance analysis of microarrays (SAM) will then be applied to the gene expression data to find genes which are differentially expressed between before and after treatment tissues.⁴⁹ The SAM statistic is similar to performing a two sample t-test for each gene under consideration, but it includes an adjustment to stabilize the coefficient of variation of the SAM statistic as a function of the standard deviation of the gene expression (across genes). As part of the SAM approach, a permutation method will be used to determine a cutoff for significance. Specifically, the permutation method takes the original data (the G x 6 matrix of expressions, where G is the number of genes) and permutes the data within each row of the expression matrix. The SAM analysis is then repeated on the permuted data. The distribution of the SAM statistics from the permuted analysis is called the "null" distribution, meaning that it is the distribution of SAM statistics we would expect to see if there were no relationship between gene expression and treatment (or, treatment modality). We then compare the distribution of the SAM statistics based on original data to the null distribution and choose a cutoff such that our false-discovery rate is 5%. That is, we choose a cutoff so that we would only expect that about 5% of the genes we claim to be differentially expressed would not be.

REFERENCES:

2. Holliday R: The inheritance of epigenetic defects. *Science* 238:163-70, 1987
3. Esteller M: Epigenetics in cancer. *N Engl J Med* 358:1148-59, 2008

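### The gene-expression analysis (12.5.4) specifies no pairing and describes another platform and sample size, and a footnote in 9.2.1 lets sites skip the only post-treatment methylation blood sample

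*Combined protocol and SAP*

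**What the plan says.** **Gene expression (12.5.4).** The aim is to find genes "differentially expressed between before and after treatment tissues". On sample size, "we will have tissue samples from between 12-41 women enrolled in this study". Section 9.1 requires material from both the diagnostic procedure and the later surgery or biopsy for every patient. The method is introduced by analogy: "The SAM statistic is similar to performing a two sample t-test for each gene under consideration". The null distribution comes from a permutation that "permutes the data within each row of the expression matrix", applied to "the G x 6 matrix of expressions, where G is the number of genes". The false-discovery rate is set at 5%.

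**Platform.** Section 9.1.3.2 names the "cDNA-mediated Annealing, Selection, Extension, and Ligation (DASL) assay from Illumina", and 12.5.4 repeats it. Section 12.5.4 then continues: "The resulting CEL files will be imported and stored on the Gene Traffic database", and "GCRMA will be applied to the CEL file results using the" Affy library.

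**Methylation (12.5.2).** Silencing is treated as categorical and its proportions are compared by Fisher's exact test, with no groups named. The sentence on gene expression is followed by t-tests and signed-rank tests of change from baseline. Exploratory objective 2 in 1.3 asks about baseline and change.

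**Methylation blood (9.2.1, 10, 10.3).** B0 or B5 is drawn before treatment, and B4 or B7 at surgery or the post-treatment biopsy. The day 15 tubes (B2, B3, B6) are for pharmacokinetics only. A footnote allows B4 or B7 to be omitted if the procedure falls within 3 days after the day 15 draw. Footnote f of both calendars, and the surgery-day and biopsy-day lists in 10.3, include the methylation sample with no exception.

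**The concern.** Exploratory objectives 2 and 4 are about change within a woman. A two-sample statistic, with arrays shuffled freely across women and time points, uses a standard error that includes between-woman variation. If a woman's two samples are positively correlated, that standard error is too large and real changes are missed. If they are negatively correlated, it is too small. An analyst cannot run 12.5.4 as written, because both the preprocessing and the permutation would have to be improvised.

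The footnote raises a different problem. An analysis can be redone, but blood that was not drawn cannot be recovered. Nothing collected on day 15 can stand in for the omitted tube, and the women concerned are those treated for the shortest time.

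**Working it through.** **1. Matrix size.** The upper limit of 41 women is consistent with 12.2: 35 + 6 = 41. Two samples per woman give 12 × 2 = 24 to 41 × 2 = 82 columns; one difference per woman gives 12 to 41. No variant gives 6, which would be three pairs. Six arrays allow C(6,3) = 20 unpaired rearrangements or 2³ = 8 sign-flips. Twelve pairs allow 2¹² = 4,096 sign-flips.

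**2. Why pairing matters.** With within-woman correlation ρ, the mean difference has variance 2σ²(1−ρ)/n. The two-sample form uses 2σ²/n. The ratio of standard errors, unpaired to paired, is 1/√(1−ρ): 1.00 at ρ = 0, 1.20 at 0.3 and 1.41 at 0.5.

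**3. SAM by simulation.** All inputs are assumptions: 2,000 independent genes, 100 of them shifted by 0.75 SD (half up, half down), and a cutoff at an estimated FDR of 5%. Unpaired means a two-sample statistic with each row permuted separately; paired means whole-patient sign-flips. Results for n = 32:

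| ρ | Changed genes found, unpaired | Paired | Realised FDR, unpaired | Paired |
|---|---|---|---|---|
| −0.2 | 0.39 | 0.23 | 0.11 | 0.04 |
| 0 | 0.37 | 0.34 | 0.04 | 0.04 |
| 0.3 | 0.34 | 0.65 | 0.003 | 0.05 |
| 0.5 | 0.26 | 0.86 | 0.000 | 0.04 |

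At n = 12 with a 1.0 SD shift, the shares found (unpaired, paired) are 0.10 and 0.07 at ρ = 0, and 0.02 and 0.50 at ρ = 0.5.

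**4. Silencing, if 12.5.2 means before versus after.** Assumed prevalence is 0.60 before and 0.35 after. Let g be the proportion of women who gain methylation. Then p01 = g, p10 = 0.25 + g, p11 = 0.35 − g, and φ = (p11 − 0.60 × 0.35)/√(0.60 × 0.40 × 0.35 × 0.65). For example, g = 0.05 gives φ = (0.30 − 0.21)/0.234 = 0.39. Exact power by multinomial enumeration, two-sided 0.05 (Fisher / McNemar):

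| φ | n = 12 | n = 32 | n = 41 |
|---|---|---|---|
| 0.60 (g = 0, most favourable) | 0.06 / 0.05 | 0.41 / 0.85 | 0.60 / 0.96 |
| 0.39 | 0.09 / 0.08 | 0.43 / 0.61 | 0.59 / 0.75 |
| 0.17 | 0.12 / 0.10 | 0.45 / 0.48 | 0.58 / 0.62 |
| 0 | 0.15 / 0.10 | 0.45 / 0.42 | 0.57 / 0.53 |
| −0.17 | 0.17 / 0.10 | 0.46 / 0.36 | 0.57 / 0.46 |

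Fisher's type I error with no change (n = 32, prevalence 50%) is 0.001 at φ = 0.60, 0.006 at 0.40, 0.033 at 0, 0.047 at −0.15, 0.052 at −0.20 and 0.072 at −0.40.

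**5. Footnote window.** The day 15 draw has a margin of ±1 day, so it falls on day 14 to 16. Adding 3 days puts the latest exempt procedure on day 19. Section 5.4 sets a minimum of three entinostat doses, the last on day 15. Section 5.5.2 prefers surgery within 3 days of the last dose, so by day 18. A first-cohort woman on that permitted path falls inside the window and may have no post-treatment methylation blood.

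**The case against.** Much of the opposing case stands.

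- The two-sample t-test is offered as an analogy, SAM has a paired form, and nothing in 12.5.4 forbids it. A reader might infer that the plan commits to an invalid analysis. The text supports only that pairing is not specified.
- A reader might infer that ignoring pairing inflates false positives. With positive correlation the unpaired analysis is conservative. Under negative correlation Fisher's size passes 0.05 only from about φ = −0.20 at n = 32. The realised SAM FDR does reach about 0.11 at ρ = −0.2, but no passage suggests that correlations are negative.
- The large power gaps need moderate to strong positive correlation. At φ = 0.17 the gain is 0.45 to 0.48, and at n = 12 McNemar gains nothing.
- A reader might infer that 12.5.2 names the wrong test. Fisher is valid for independent groups, and the closing change-from-baseline sentence could be read to cover methylation too, since 9.1.3.3 describes QM-MSP as quantitative. But the paragraph calls silencing categorical and attaches that sentence to expression, so the comparison stays unnamed.
- The footnote can be read as a specific exception to a general schedule, and it permits omission without requiring it. The preferred timings (22 days, or close to 29 days) fall outside its window, tissue methylation is unaffected, and the number of women concerned is unknown. None of this changes the fact that the day 15 tubes cannot replace the omitted one.
- Section 9.1.3.2 already calls for RT-PCR checks and independent samples. Those can follow up only the genes that the first analysis finds.

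**Conclusion.** The point holds as a gap in specification for exploratory objectives 2 and 4, of minor to moderate weight. No primary endpoint, stopping rule or safety rule is touched, and a reader should not infer that the trial's main conclusion is at risk.

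Three parts need no assumed effect size or correlation: 12.5.4 states no pairing; its matrix size and CEL/GCRMA/Affy steps do not match the sample size and assay that the protocol names; and the 9.2.1 footnote is not reconciled with the calendars and 10.3 and can remove the only post-treatment methylation blood. That the named preprocessing belongs to another platform is general knowledge of the field.

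The size of the pairing effect rests on assumed prevalences, shifts and correlations, and for SAM on independent genes. At n = 32 it runs from a loss of about 0.03 at zero correlation to a large gain at clearly positive correlation (0.43 to 0.61 for silencing at φ = 0.39; 0.26 to 0.86 for SAM at ρ = 0.5). The 12.5.2 point is subsidiary: an unnamed comparison that becomes a wrong test under only one reading.

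**What to change.** - **12.5.4:** specify paired SAM, with sign-flips applied to a whole patient at a time, on the actual number of complete pairs. Remove the six-column matrix. Replace the CEL, GCRMA and Affy steps with preprocessing suited to Illumina bead arrays.
- **9.2.1:** delete the footnote, so that the draw already in the calendars and 10.3 is always taken, and check that the three places then agree.
- **12.5.2:** name the groups. For before versus after silencing, use exact McNemar or the signed-rank test on the quantitative QM-MSP values. Keep Fisher for named independent groups, such as anastrozole versus tamoxifen.

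The cost is wording in three places, with no new visit and no draw beyond those scheduled. If within-woman correlation is near zero, a little power is lost at n = 32: 0.45 to 0.42 for silencing and 0.37 to 0.34 for SAM.

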APPENDIX A: ECOG Performance Status Scale

Grade	Descriptions
0	Normal activity. Fully active, able to carry on all pre-disease performance without restriction.
1	Symptoms, but ambulatory. Restricted in physically strenuous activity, but ambulatory and able to carry out work of a light or sedentary nature (e.g., light housework, office work).
2	In bed <50% of the time. Ambulatory and capable of all self-care, but unable to carry out any work activities. Up and about more than 50% of waking hours.
3	In bed >50% of the time. Capable of only limited self-care, confined to bed or chair more than 50% of waking hours.
4	100% bedridden. Completely disabled. Cannot carry on any self-care. Totally confined to bed or chair.
5	Dead.

APPENDIX B: American Joint Committee on Cancer Staging (AJCC)

T – Primary Tumor	
TX	Primary tumor cannot be assessed
T0	No evidence of primary tumor
Tis	Carcinoma in situ
Tis (DCIS)	Ductal carcinoma in situ
Tis (LCIS)	Lobular carcinoma in situ
Tis (Paget)	Paget's disease of the nipple with no tumor Note: Paget's disease associated with a tumor is classified according to the size of the tumor.
T1	Tumor ≤ 2 cm in greatest dimension
T1mic	Microinvasion ≤ 0.1 cm in greatest dimension
T1a	Tumor > 0.1 cm but not > 0.5 cm in greatest dimension
T1b	Tumor > 0.5 cm but not > 1 cm in greatest dimension
T1c	Tumor > 1 cm but not > 2 cm in greatest dimension
T2	Tumor > 2 cm but not > 5 cm in greatest dimension
T3	Tumor > 5 cm in greatest dimension
T4	Tumor of any size with direct extension to (a) chest wall or (b) skin, only as described below
T4a	Extension to chest wall, not including pectoralis muscle
T4b	Edema (including peau d'orange" or ulceration of the skin of the breast, or satellite skin nodules confined to the same breast
T4c	Both T4a and T4b
T4d	Inflammatory carcinoma

N – Regional lymph nodes	
NX	Regional lymph nodes cannot be assessed (e.g., previously removed)
N0	No regional lymph node metastasis
N1	Metastasis in movable ipsilateral axillary lymph node(s)
N2	Metastases in ipsilateral axillary lymph nodes fixed or matted, or in clinically apparent ipsilateral internal mammary nodes in the absence of clinically evident axillary lymph node metastasis
N2a	Metastasis in ipsilateral axillary lymph nodes fixed to one another (matted) or to other structures
N2b	Metastasis only in clinically apparent ipsilateral internal mammary nodes and in the absence of clinically evident axillary lymph node metastasis
N3	Metastasis in ipsilateral infraclavicular lymph node(s), or in clinically apparent ipsilateral internal mammary lymph node(s) and in the presence of clinically evident axillary lymph node metastasis; or metastasis in ipsilateral supraclavicular lymph node(s) with or without axillary or internal mammary lymph node involvement
N3a	Metastasis in ipsilateral infraclavicular lymph node(s) and axillary lymph node(s)
N3b	Metastasis in ipsilateral internal mammary lymph node(s) and axillary lymph node(s)
N3c	Metastasis in ipsilateral supraclavicular lymph node(s)

APPENDIX B (Continued)

pN – Regional lymph nodes	
pNX	Regional lymph nodes cannot be assessed (e.g., previously removed or not removed for pathologic study)
pN0	No regional lymph node metastasis histologically, no additional examination for isolated tumor cells
pN0(i-)	No regional lymph node metastasis histologically, negative IHC
pN0(i+)	No regional lymph node metastasis histologically, positive IHC, no IHC cluster > 0.2 mm
pN0(mol-)	No regional lymph node metastasis histologically, negative molecular findings (RT-PCR)
pN0(mol+)	No regional lymph node metastasis histologically, positive molecular findings (RT-PCR)
pN1mi	Micrometastasis (> 0.2 mm, none > 2.0 mm)
pN1	Metastasis in one to three axillary lymph nodes and/or in internal mammary nodes with microscopic disease detected by sentinel lymph node dissection but not clinically apparent
pN1a	Metastasis in one to three axillary lymph nodes
pN1b	Metastasis in internal mammary nodes with microscopic disease detected by sentinel lymph node dissection but not clinically apparent
pN1c	Metastasis in one to three axillary lymph nodes and in internal mammary lymph nodes with microscopic disease detected by sentinel lymph node dissection but not clinically apparent
pN2	Metastasis in four to nine axillary lymph nodes, or in clinically apparent internal mammary lymph nodes in the absence of axillary lymph node metastasis
pN2a	Metastasis in four to nine axillary lymph nodes (at least one tumor deposit > 2.0 mm)
pN2b	Metastasis in clinically apparent internal mammary lymph nodes in the absence of axillary lymph node metastasis
pN3	Metastasis in 10 or more axillary lymph nodes, or in infraclavicular lymph nodes, or in clinically apparent ipsilateral internal mammary lymph nodes in the presence of one or more positive axillary lymph nodes; or in more than three axillary lymph nodes with clinically negative microscopic metastasis in internal mammary lymph nodes; or in ipsilateral supraclavicular lymph nodes
pN3a	Metastasis in 10 or more axillary lymph nodes (at least one tumor deposit > 2.0 mm), or metastasis to the infraclavicular lymph nodes
pN3b	Metastasis in clinically apparent ipsilateral internal mammary lymph nodes in the presence of one or more positive axillary lymph nodes; or in more than three axillary lymph nodes and in internal mammary lymph nodes with microscopic disease detected by sentinel lymph node dissection but not clinically apparent
pN3c	Metastasis in ipsilateral supraclavicular lymph nodes

M – Distant metastasis	
MX	Distant metastasis cannot be assessed
M0	No distant metastasis
M1	Distant metastasis

APPENDIX C: Study Drug Diary

Study Drug Diary: Entinostat

Please complete this diary every time you take your entinostat. You should also use this diary to record any side effects that you experience and medications that you take other than your study drugs (entinostat and anastrozole or tamoxifen). Please be sure to bring this diary with you to your next doctor's visit.

You will take entinostat once a week until you have your surgery (i.e. lumpectomy or mastectomy). Entinostat is a tablet either in light brown (1 mg) or intense yellow (5 mg). Entinostat should be taken with a meal after the first two or three bites.

You are currently taking:

3 mg of entinostat weekly

5 mg of entinostat weekly

Please contact your study doctor or nurse with any new complaints or symptoms that you have after starting to take entinostat. If you have severe symptoms, your dose of entinostat may be changed or you may be told to stop taking entinostat. Please do not make any changes in your entinostat dose without speaking with your study doctor or nurse.

Dose #	Due Date	Due Time	Date Taken	Time Taken	# of Pills Taken	Comments (Side effects, complaints, other medications)
1						
2						
3						
4						
5						

Note: For any time that you did not take your entinostat (Example: You forgot to take it), write the reason that you did not take it in the "Comments" field.

Completed by: _____
Signature of Patient

Date: _____

Reviewed by: _____
Signature of Study Staff

Date: _____

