5.1.1 Entinostat

Entinostat is supplied as light brown (1 mg) or intense yellow (5 mg) coated tablets. Patients will self-administer entinostat as per assigned dose level shown in section 6.1. Tablets should be taken with a meal after the first two or three bites. If the patient's dose requires more than one tablet, the tablets should be taken one at a time. Unused tablets or empty bottles will be returned to the clinic for accountability purposes. Dose reductions for toxicity are summarized in section 6.2. The definitive surgery or post-treatment biopsy (biopsy#2) must take place within 6 days (preferably within 3 days) after the last dose of entinostat.

Entinostat may cause fatigue or malaise; advise patient to exercise caution while driving a vehicle or operating machinery. Delay administration of H₂-antagonists, antacids, or proton pump inhibitors, or other drugs that lower acidity for at least 2 hours after dosing entinostat.

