6.1.1 Non-Hematologic Toxicities of Entinostat

The following rules will be followed for the management of adverse events that are definitely or probably due to entinostat alone. Grades are according to the active version of NCI CTCAE as per section 7.3.

Toxicity	Hold dose	Treatment	Recovery	Dose reduction
Grade ≥ 3	Until recovery to grade 1 or baseline	Symptomatic remedies, start prophylaxis	If recovered by next scheduled dose	Resume at one dose level below the current dose
			If not recovered by next scheduled dose	Skip this dosing; resume at one dose level below the current dose after recovery
Recurrent Grade ≥ 3 despite dose reduction	Until recovery to grade 1 or baseline	Symptomatic remedies, start prophylaxis	If recovered by next scheduled dose	Resume at one dose level below the current dose
			If not recovered by next scheduled dose	Skip this dosing; resume at one dose level below the current dose every other week after recovery
Grade ≤ 2	Until recovery to grade 1 or baseline	Symptomatic remedies, start prophylaxis	If recovered by next scheduled dose	Resume at the current dose level
			If not recovered by next scheduled dose	Skip this dosing; resume at the current dose after recovery

The dose modification schemas are as follow for both postmenopausal and premenopausal women:

Dose Modification Schema for Postmenopausal Women		
Dose Level	Dose	
	Entinostat (mg)	Anastrozole (mg) daily
-1	3 mg weekly (on day 1, 8, 15, 22, and 29)	1
1	5 mg weekly (on day 1, 8, 15, 22, and 29)	1

or

Dose Modification Schema for Premenopausal Women		
Dose Level	Dose	
	Entinostat (mg)	Tamoxifen (mg) daily
-1	3 mg weekly (on day 1, 8, 15, 22, and 29)	20
1	5 mg weekly (on day 1, 8, 15, 22, and 29)	20

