6.1.2 Hematologic Toxicities of Entinostat

Myelosuppression is a common side effect of higher doses of entinostat. The guidelines in the table below will be followed for hematologic toxicities.

ANC at planned dose	PLT at planned dose	Cycle Delivery
≥ 1.0 x 10 ⁹ /L	and ≥ 80 x 10 ⁹ /L	Resume at the current dose level
< 1.0 x 10 ⁹ /L	or < 80 x 10 ⁹ /L	Delay until recovery to grade 1 or

baseline

If the treatment is delayed for more than 2 weeks, the patient will be discontinued from treatment and followed until event resolution, and treated off-protocol at the investigator's discretion.

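### The entinostat diary prints weekly dosing only, while one branch of section 6.1.1 resumes the drug every other week; the two texts need to be reconciled

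*Combined protocol and SAP*

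**What the plan says.** **Diary (Appendix C, entinostat sheet).** The instruction to the patient reads "You will take entinostat once a week until you have your surgery (i.e. lumpectomy or mastectomy". Below it are two options for the current dose, "3 mg of entinostat weekly" and "5 mg of entinostat weekly". The log has five dose rows, each with blank columns for due date and due time.

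**Section 6.1.1.** The table has a row headed "Recurrent Grade ≥ 3 despite dose reduction". If the patient has recovered by the next scheduled dose, the row lowers the dose level and does not mention the interval. If she has not, the instruction is "Skip this dosing; resume at one dose level below the current dose every other week after recovery". The schema printed under the table defines two levels, both weekly. The lower one, level -1, is "3 mg weekly (on day 1, 8, 15, 22, and 29".

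**Section 5.1.1.** "Patients will self-administer entinostat as per assigned dose level", with section 6.1 named as the place where the dose levels are shown.

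**Duration and visits.** First-cohort treatment lasts 15 to 29 days, preferably 22 (sections 5.1 and 5.4). Second-cohort treatment runs to progression. Visits after the second biopsy are 4-weekly or at the physician's discretion (section 10, second-cohort calendar, and section 10.3).

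**The concern.** The diary is the written instruction that the patient holds for a drug she takes herself. It can name two regimens, and the protocol contains a third. The mismatch falls on patients who have already had grade 3 or higher toxicity twice, the second time after a reduction.

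If such a patient follows the printed text, she takes entinostat twice as often as 6.1.1 orders. Any later adverse event would then be attributed to a schedule she was not actually on. The risk is greatest in the second cohort, where treatment is open-ended and scheduled contact becomes less frequent after the second biopsy.

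**Working it through.** The plan gives no figure on this point, so there is none to reproduce. The check compares the two texts and counts doses.

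**1. Frequency ratio.** Diary: 1 dose per 7 days. Branch of 6.1.1: 1 dose per 14 days. Ratio = (1/7) ÷ (1/14) = 2.

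**2. Earliest route into the branch on the nominal calendar.**

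| Day | Event |
|---|---|
| 1 | 5 mg; grade ≥3 toxicity, recovered by day 8 |
| 8 | 3 mg; toxicity recurs, not recovered by day 15 |
| 15 | dose skipped |
| 22 | resumption, every other week |

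The delay is 7 days, inside the 2-week limit in sections 5.8, 6.1.2 and 10.3. The patient would therefore still be on treatment, and the branch can be reached.

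**3. First cohort (29-day maximum).** From resumption the diary implies doses on days 22 and 29. Section 6.1.1 implies day 22 and then day 36, which lies past the maximum. The excess is one dose. At the preferred 22-day duration it is zero.

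The effect on total dose to day 29 can be counted on the assumption that the resumed dose stays at 3 mg. This is for arithmetic only, because 6.1.1 does not define that dose. Printed: 5 + 3 + 3 + 3 = 14 mg. Ordered: 5 + 3 + 3 = 11 mg. Ratio = 14/11 = 1.27.

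**4. Second cohort.** Per 28 days, printed doses = 28/7 = 4 and ordered doses = 28/14 = 2. That 28-day span is also the nominal gap between visits after the second biopsy.

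**5. The dose in the same row.** A patient reduced from level 1 (5 mg) to level -1 (3 mg) who has a recurrence must go one level lower. The schema stops at level -1, so the dose that goes with the every-other-week interval is undefined.

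**6. Does any other diary text state the interval?** The sheet says that the dose may be changed or the drug stopped, but it does not mention a change of interval. It names surgery as the only end of treatment, so its wording was not adapted to second-cohort patients, for whom the 2:1 mismatch would persist.

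**The case against.** **The form has safeguards.** The due-date column can carry any interval. The sheet describes what the patient is currently taking, asks her not to change the dose without speaking to the study team, and has a staff review signature. With five rows, a second-cohort patient will need new sheets, which gives staff a chance to correct the schedule. Section 5.1.1 ties self-administration to section 6.1, so the diary does not formally override it. All of this stands, and it is why the printed frequency *can* mislead rather than must. However, no section says who fills in the due dates or that they take precedence. A sheet with fortnightly dates beside a weekly option would contradict itself.

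**The branch is narrow.** It covers only events definitely or probably due to entinostat alone, after a reduction, a recurrence and non-recovery. Recurrent grade 3 or 4 diarrhea is handled separately in section 6.2.2, and longer delays lead off treatment. This also stands and limits the number affected. That the row lacks a defined dose is a second defect in it. It does not remove the ordered interval.

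**Stronger readings that the documents do not support.**
- A reader might infer that the diary also conflicts with every skip and hold rule, including the section 6.1.2 table that works from "ANC at planned dose". Through day 29, blood counts, chemistries and entinostat administration are listed for the same weekly visits, and the diary's closing note provides for recording doses not taken. A diary need not restate each hold rule.
- A reader might infer that a patient's whole cumulative dose is doubled. The doubling starts only at resumption.
- A reader might compare pre-dose drug levels on the two schedules and find a much larger ratio. That mostly reflects sampling 7 rather than 14 days after a dose. At an unchanged dose, average exposure differs by a factor of 2.

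**Conclusion.** The contradiction is on the face of the text: Appendix C allows weekly dosing only, and one branch of 6.1.1 orders every other week. For patients in that branch the printed frequency is twice the ordered one from resumption onward. This means at most about one extra dose in the first cohort, and 4 against 2 doses per 28 days in the second.

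These counts assume the nominal dosing days and a patient who follows the printed text rather than any dates written by staff. The documents give no basis for estimating how many patients will enter the branch, beyond the fact that its conditions are restrictive.

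This is a patient-safety inconsistency between a form and a rule. It does not touch the two-stage design, the endpoints or their analysis. It is worth correcting because it concerns patients who tolerate the drug poorly and because the correction is small. No view is taken on which schedule is right.

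**What to change.** Reconcile Appendix C with section 6.1.1 so that both state the same schedule. There are two routes, and the sponsor must choose:

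- **If the every-other-week interval is intended:** replace the fixed weekly wording in the diary with fields completed by study staff (assigned dose, assigned interval, effective date), and issue a new sheet at each change.
- **If only weekly dosing is intended:** amend the branch in 6.1.1 and leave the diary's weekly options in place.

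In the same edit, resolve the 6.1.1 row's call for a level below the current dose, given that the schema defines none below level -1.

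The cost is a reworded one-page form, or a table cell, in the next amendment, plus reissuing sheets when a regimen changes. No patients, visits or procedures are added, and no dose, interval or new dosing rule is proposed here.
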